4.4. End of Study Definition

The end of the study is defined as the date of the last visit of the last participant in the study or last scheduled procedure shown in the SoA for the last participant in the study globally.

A participant is considered to have completed the study if he/she has completed all visits in the study including the last visit.

5. Study Population

Prospective approval of protocol deviations to recruitment and enrollment criteria, also known as protocol waivers, is not permitted.

Participants who have completed the lead-in Phase 2 (LIN-MD-62 or LIN-MD-63) or Phase 3 (LIN-MD-64) studies must meet all the inclusion and exclusion criteria as described in the following sections.

Where applicable for this pediatric population, the term “participant” refers to the participant, parent, guardian, legally authorized representative (LAR), and/or caregiver.

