8.3.1. Adverse Events of Special Interest

AESIs are defined as significant volume depletion and/or significant electrolyte abnormalities and/or ECG abnormalities that are considered by the investigator or sponsor to be related to diarrhea. The investigator should contact the sponsor if there is any question whether the criterion for an AE of special interest has been met. All AESIs must be reported to the sponsor as described in [Appendix 3](#).

8.3.2. Time Period and Frequency for Collecting Adverse Events, Serious Adverse Events, and Adverse Events of Special Interest Information

At each visit, participants are to be queried regarding any AEs or SAEs that have occurred since the previous visit. Participants will be asked to volunteer information with a nonleading question such as, "How do you feel since your last visit?" Study site personnel will record all pertinent information in the participant's eCRF.

- All SAE from the signing of the ICF until 30 days after the last dose of study intervention will be collected at the timepoints specified in the SoAs (Section [1.4](#) and Section [1.5](#)), and as observed or reported spontaneously by study participants.
- All AEs from the signing of the ICF until 30 days after the last dose of study intervention will be collected at the timepoints specified in the SoAs (Section [1.4](#) and Section [1.5](#)), and as observed or reported spontaneously by study participants.

- Medical occurrences that begin before the start of study intervention, but after obtaining informed consent will be recorded in the AE section of the eCRF.

All SAEs (including serious AESIs) will be recorded and reported to the sponsor or designee within 24 hours on an SAE form, as indicated in [Appendix 3](#). Nonserious AESIs do not require submission on an SAE form; rather, these events only need to be entered into the eCRF. The investigator will submit any updated SAE data to the sponsor within 24 hours of it being available.

Investigators are not obligated to actively seek AE or SAE information after conclusion of the study participation. However, if the investigator learns of any SAE including a death, at any time after a participant has been discharged from the study, and he/she considers the event to be reasonably related to the study intervention or study participation, the investigator must promptly notify the sponsor.

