The method of recording, evaluating, and assessing causality of AEs and SAEs and the procedures for completing and transmitting SAE reports are provided in [Appendix 3](#).

8.3.3. Method of Detecting Adverse Events, Serious Adverse Events, and Adverse Events of Special Interest

Care will be taken not to introduce bias when detecting AEs and/or SAEs. Open-ended and nonleading verbal questioning of the participant is the preferred method to inquire about AE occurrences.

8.3.4. Follow-up of Adverse Events, Serious Adverse Events, and Adverse Events of Special Interest

After the initial AE/SAE report, the investigator is required to proactively follow each participant at subsequent visits/contacts. All AE/SAE and non-serious AESIs (as defined in [Appendix 3](#)) will be followed until resolution, stabilization, the event is otherwise explained, or the participant is lost to follow-up (as defined in Section [7.3](#)). If a follow-up visit is deemed necessary for appropriate safety surveillance, it will take place within 30 days of the final protocol-defined study visit.

The investigator is obligated to perform or arrange for the conduct of supplemental measurements and/or evaluations as medically indicated or as requested by the sponsor to elucidate the nature and/or causality of the AE or SAE as fully as possible. This may include

additional laboratory tests or investigations, histopathological examinations, or consultation with other health care professionals.

New or updated information will be recorded in the originally completed eCRF.

The investigator will submit any updated SAE data to the sponsor within 24 hours of receipt of the information.

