9.4.1. Adverse Events

AEs will be coded using the Medical Dictionary for Regulatory Activities (MedDRA), Version 23.0 or newer.

An AE will be considered a TEAE if:

- The AE began on or after the date of the first dose of study intervention in LIN-MD-66; or
- The AE was present before the date of the first dose of study intervention in LIN-MD-66 but increased in severity or became serious on or after the date of the first dose of study intervention in LIN-MD-66.

An AE that occurs more than 1 day after the last dose of study intervention in LIN-MD-66 will not be counted as a TEAE.

An AE will be considered a treatment-emergent SAE (TESAE) if it is a TEAE that additionally meets any SAE criteria.

The number and percentage of participants reporting TEAEs in each study intervention group will be tabulated by SOC and preferred term and by SOC, preferred term, and severity.

The number and percentage of participants reporting treatment-related TEAEs in each study intervention group will be tabulated by SOC and preferred term.

If more than 1 AE is coded to the same preferred term for the same participant, the participant will be counted only once for that preferred term using the most severe and most related occurrence for the summarizations by severity and by relationship to study intervention.

Summary tables will be provided for participants with TESAEs, AESIs, and participants with TEAEs leading to discontinuation if 5 or more participants reported such events. Listings of all AEs, SAEs, AESIs, and AEs leading to discontinuation by participant will be presented.

The definitions of an AE and SAE can be found in [Appendix 3](#).

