10.3.1. Definition of AE

AE Definition

• An AE is any untoward medical occurrence in a patient or clinical study participant, temporally associated with the use of study intervention, whether or not considered related to the study intervention.• An AE can therefore be any unfavorable and unintended sign (including an abnormal laboratory finding), symptom, or disease (new or exacerbated) temporally associated with the use of study intervention. 
For the purpose of the site's data collection responsibilities, any untoward event that was reported from the time written consent was obtained until 30 days after the final protocol-defined study visit (or the last known dose of study intervention if the final visit does not occur) is to be considered an AE. Particular attention must be given to the AE of diarrhea, which was the most frequently reported AE in the adult linaclotide program. Details about AE reporting are provided below.
 
Examples of AEs are as follows:
 
• Changes in the general condition of the participant• Subjective symptoms offered by or elicited from the participant• Objective signs observed by the investigator or other study site personnel• All diseases that occur after signing the informed consent, including any change in severity or frequency of pre-existing disease• All clinically relevant abnormalities in laboratory values or clinically relevant physical findings that occur during the study schedule 
Please note medical procedures scheduled prior to consenting, but occurring during the study should not be captured as AEs, but should be listed in the medical history if related to a pre-existing condition.
 
AE of Special Interest (AESI)
 
An AESI (serious or nonserious) is one of scientific and medical concern specific to the sponsor's study intervention or program, which warrants ongoing monitoring and rapid

communication by the investigator to the sponsor. Such an event might warrant further investigation in order to characterize and understand it.

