9.2.1 Treatment-Emergent Adverse Events

An AE will be considered a treatment emergent adverse event (TEAE) if:

- The AE began on or after the date of the first dose of study intervention in LIN-MD-66; or
- The AE was present before the date of the first dose of study intervention in LIN-MD-66 but increased in severity or became serious on or after the date of the first dose of study intervention in LIN-MD-66.

However, an AE that occurs more than 30 days after the last dose of study intervention in LIN-MD-66 will not be counted as a TEAE.

An AE will be considered a treatment emergent serious adverse event (TESAE) if it is a TEAE that additionally meets any serious adverse event (SAE) criterion.

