12.0 Version History

Table 2. SAP Version History Summary

Version	Date	Summary
1.0	08 Nov 2021	Original version
2.0	19 Jul 2022	
Clarified study drug duration summary categories.Added summary for total continuous exposure of linaclotide across lead-in studies and long-term safety study.Modified TEAE definition to include any AE that occurs within 30 days (instead of 1 day) after the last dose of study intervention.Added Exposure-Adjusted Incidence Rate (EAIR) analysis for TEAE overview and TEAE by SOC and PT.Added additional analyses for Diarrhea TEAE.Included age of 18 years old in PCS criteria for clinical laboratory parameters, vital signs, and ECG parameters.

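### TEAEs are counted to 30 days after the last dose, but no AE contact is scheduled after the end-of-treatment visit, so late events in completers rest on spontaneous report and are pooled unlabelled with solicited ones

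*SAP*

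**What the plan says.** **TEAE window.** SAP Section 9.2.1: "an AE that occurs more than 30 days after the last dose of study intervention in LIN-MD-66 will not be counted as a TEAE". Protocol Section 9.4.1: "An AE that occurs more than 1 day after the last dose of study intervention in LIN-MD-66 will not be counted as a TEAE". The SAP change was deliberate; its Section 12.0 records "Modified TEAE definition to include any AE that occurs within 30 days (instead of 1 day) after the last dose of study intervention".

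**AE collection.** Protocol Section 8.3.2: "All AEs from the signing of the ICF until 30 days after the last dose of study intervention will be collected at the timepoints specified". The sentence goes on to name the schedules of activities as the source of those timepoints, and to add events that are observed or that participants report on their own initiative. The same section says: "Investigators are not obligated to actively seek AE or SAE information after conclusion of the study participation". Section 4.4 says: "A participant is considered to have completed the study if he/she has completed all visits in the study including the last visit".

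**Last scheduled contact.** In Tables 1-1 and 1-2 (FC) the final AE evaluation is Visit 7/EOT, Day 169 (+3). In Tables 1-3 and 1-4 (IBS-C) it is Visit 10/EOT, Day 365 (+3). Appendix 10 also ends there. After that, Section 8.3.4 provides only: "If a follow-up visit is deemed necessary for appropriate safety surveillance, it will take place within 30 days of the final protocol-defined study visit".

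**Reporting.** SAP Sections 9.2.2 and 9.2.3 tabulate all TEAEs together. Section 9.2.4 defines the exposure-adjusted incidence rate (EAIR) with treatment duration as the time at risk for a participant without the event.

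**The concern.** Widening the TEAE window from 1 to 30 days changed the analysis but not the data collection. Up to EOT, site staff ask about AEs at every visit. After EOT no scheduled timepoint remains, so of the two routes in protocol Section 8.3.2 only unprompted observation and reporting is left. The optional follow-up visit cannot find a new event that nobody has mentioned.

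Safety is the sole primary objective and the TEAE tables are its main output. Those tables would combine two kinds of ascertainment without telling the reader. The EAIR adds a second mismatch, because events from the post-treatment days enter the numerator while participants without the event contribute none of those days to the denominator.

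**Working it through.** The plan gives no figure to reproduce: there is no hypothesis, and the sample size has no statistical basis. The check is day arithmetic, followed by an illustration that needs assumptions.

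**1. Days with no scheduled query (completers).** Treatment lasts 24 weeks = 168 days (FC) or 52 weeks = 364 days (IBS-C). The last dose falls between the final day of that period and the EOT day. Uncovered days = 30 − (EOT day − last-dose day).

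| | Last dose on day | EOT on day | Uncovered days |
|---|---|---|---|
| FC, earliest EOT | 168 | 169 | 29 (96.7%) |
| FC, latest EOT | 168 | 172 | 26 (86.7%) |
| IBS-C, earliest EOT | 364 | 365 | 29 (96.7%) |
| IBS-C, latest EOT | 364 | 368 | 26 (86.7%) |
| Either, dose on EOT day | = EOT day | any | 30 (100%) |

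The range is 26 to 30 of 30 days.

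**2. Share of the whole TEAE period.** FC: 30/(168 + 30) = 15.2%. IBS-C: 30/(364 + 30) = 7.6%. These are shares of calendar time, not of events.

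**3. Illustration of events in the window (assumed rates).** The documents give no post-treatment event rate and no capture fraction. If all 120 planned participants completed, the window would hold 120 × 30/365.25 = 9.9 person-years. With a constant rate λ per year, the expected number with at least one event in the window is 120 × (1 − exp(−λ × 30/365.25)).

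| Assumed rate per 100 patient-years | With an event in the window | Unrecorded at 50% capture | Unrecorded at 25% capture |
|---|---|---|---|
| 25 | 2.4 | 1.2 | 1.8 |
| 50 | 4.8 | 2.4 | 3.6 |
| 100 | 9.5 | 4.7 | 7.1 |
| 200 | 18.2 | 9.1 | 13.6 |

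**4. Effect on the planned summaries (assumed rate of 50 per 100 patient-years throughout, full treatment duration).**

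| Window events captured | FC crude % | FC EAIR | IBS-C crude % | IBS-C EAIR |
|---|---|---|---|---|
| None | 20.5 | 50.0 | 39.2 | 50.0 |
| Half | 22.1 | 53.8 | 40.5 | 51.5 |
| All | 23.7 | 57.6 | 41.7 | 53.0 |

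The crude percentage is 1 − exp(−λ × treatment time), plus the captured fraction of first events in the next 30 days. The EAIR divides that by treatment time at risk, plus the days from last dose to onset for captured window events, as the onset formula in SAP Section 9.2.4 implies. If time at risk is capped at treatment duration instead, full capture gives 57.8 (FC) and 53.1 (IBS-C).

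Two things follow. Under-capture lowers the 30-day crude incidence relative to full capture, but not below the on-treatment value. The EAIR departs from the assumed true rate of 50 as capture improves, because the numerator gains events with almost no matching time.

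**The case against.** The strongest reply is that collection is passive, not absent. Protocol Section 8.3.2 accepts spontaneous reports to day 30, and Appendix 3 makes AEs part of the site's data collection until 30 days after the final visit. AEs open at the final visit are followed to resolution or stabilization. Clinically significant laboratory values within 30 days of the last dose are repeated, and pregnancies and potential Hy's law cases are reportable over the same period. That all stands. A reader might infer that nobody asks at all, and the documents do not support it. Nor does Section 4.4 strictly define when participation concludes, so an end to the duty to ask at EOT is an inference. None of these provisions, however, supplies a scheduled query for new events.

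A reader might also infer that the post-treatment window will look falsely safe. No planned output shows that window on its own, and relative to the protocol's 1-day rule the SAP can only add events. Nor can it be said that the study fails a post-treatment objective, because none is stated; the objective is long-term safety over 24 or 52 weeks of exposure.

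Early discontinuers must return for EOT, which may fall inside the window, so ascertainment could differ from that in completers. The documents give no timing for those returns, so this is only a possibility.

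The different anchor in Appendix 3 (final visit, not last dose) loses nothing. For completers it is equal to or up to 4 days longer than the Section 8.3.2 period, and shortening it would discard information.

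**Conclusion.** The mismatch holds. In completers, 26 to 30 of the 30 post-treatment days in the SAP's TEAE window (87–100%) have no scheduled AE query, so new-onset events there are likely under-counted by an amount the documents cannot fix. The day count assumes that visits fall within their stated windows and that dosing runs to the end of the period or to EOT. The event counts and rates in the illustration rest on assumed hazards and capture fractions, and the counts also assume 120 completers.

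The planned TEAE tables do not separate these events from solicited ones. The EAIR numerator includes them while its denominator omits the window for event-free participants. Protocol and SAP state different TEAE windows. On-treatment TEAE counts are unaffected, and overall rates are not pulled below their on-treatment values. This is a limited weakness, worth correcting because the correction is cheap.

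**What to change.** 1. Add one phone contact for AEs, SAEs and pregnancy at about 30 days after the last dose to Tables 1-1 to 1-4, modelled on the Week 2 phone visit. It reduces the unsolicited stretch in completers to about zero. Cost: a protocol amendment and one call per participant by existing staff.
2. For participants already past EOT, or if there is no amendment, tabulate TEAEs in SAP Sections 9.2.2 and 9.2.3 to last dose plus 1 day, and show onsets on days 2 to 30 separately, labelled as not systematically solicited. Cost: one extra column or table, with no site burden.
3. In SAP Section 9.2.4, base the EAIR on events to last dose plus 1 day, so that numerator and time at risk match to within a day. This is needed even if the call is added, because the call alone does not change the denominator.
4. Reconcile protocol Section 9.4.1 (1 day) with SAP Section 9.2.1 (30 days), and state which window each table uses.
5. Leave the Appendix 3 collection period at its present length.

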9.2.2 Adverse Event Overview

Overall summary of TEAEs will be provided on a per-participant level for TEAEs, treatment-related TEAEs, TESAEs, deaths, and TEAEs leading to study intervention discontinuation.

If there is more than one event for the same participant, the participant will be counted only once.

9.2.3 Treatment-Emergent Adverse Events by SOC and/or PT

The number and percentage of participants reporting TEAEs will be tabulated by SOC and preferred term; and by SOC, preferred term, and severity.

The number and percentage of participants reporting treatment-related TEAEs will be tabulated by SOC and preferred term.

If more than one event is coded to the same preferred term for the same participant, the participant will be counted only once for that preferred term using the greatest severity for the summarization by severity.

If the severity of a TEAE is missing, the maximum severity will be assigned to the event for the summarization by severity. The value will be displayed as missing in the data listing.

If the relationship to the study intervention is missing for a TEAE, the event will be considered related to the study intervention for the summarization. The value will be displayed as missing in the data listing.

Listings of all the AEs will be presented.

9.2.4 Treatment-Emergent Adverse Events Exposure-Adjusted Incidence Rate (EAIR)

The EAIR provides exposure adjusted rates for the first occurrence of an event. It is an adjusted incidence rate calculated as 100 times the number of subjects with the specific event divided by the total time at risk (in year) among subjects included in the analysis. For a specific event, subjects with multiple occurrences of the event in the specific analysis period will only be counted once in the numerator. The time at risk for a subject without the specific event is the treatment duration, whereas the time at risk for a subject with the event is defined as the treatment duration up to the start date (inclusive) of the first occurrence of the event (date of first onset of the event – date of first dose + 1). The total time at risk in years (denominator) is calculated as dividing the sum of time at risk in days over all subjects included in the analysis by 365.25. The EAIR per 100 patient-years, calculated as [numerator/denominator]*100, is interpreted as the expected number of subjects with at least one occurrence of the specific event per 100 patient-years of exposure to the study drug.

The EAIR per 100 patient-years will be provided for each AE category in the AE overview summary and for the TEAE summary by SOC and PT.

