6.0 Study Drug Duration and Compliance

For the safety population, duration of treatment will be summarized for each study intervention group overall and for each age group (6 to 11 years and 12 to 18 years in FC and 7 to 11 years and 12 to 18 years in IBS-C) separately for FC and IBS-C participants. Duration of treatment is defined for each participant as last dose date minus first dose date + 1 in this study. Duration of treatment will be summarized using the number of participants treated, mean, standard deviation, median, minimum and maximum. In addition, the number and percentage of participants in each treatment duration category (defined below) will be summarized.

- FC participants: ≤ 4 weeks, $> 4 - \leq 8$ weeks, $> 8 - \leq 12$ weeks, $> 12 - \leq 18$ weeks, $> 18 - \leq 24$ weeks, > 24 weeks
- IBS-C participants: ≤ 4 weeks, $> 4 - \leq 8$ weeks, $> 8 - \leq 12$ weeks, $> 12 - \leq 20$ weeks, $> 20 - \leq 28$ weeks, $> 28 - \leq 36$ weeks, $> 36 - \leq 44$ weeks, $> 44 - \leq 52$ weeks, > 52 weeks

Additionally, total continuous exposure with any linaclotide doses across the lead-in studies and Study LIN-MD-66 will also be summarized. Participants who received linaclotide, completed the lead-in study, and enrolled in Study LIN-MD-66 within 28 days from last study intervention will be considered to have continuous exposure. The continuous exposure of linaclotide will be calculated as the sum of the exposure from the lead-in study and from Study LIN-MD-66. The number and percentage of participants in each treatment duration category (defined below) will be summarized.

- FC participants: ≥ 4 weeks, ≥ 12 weeks, ≥ 24 weeks, ≥ 30 weeks, ≥ 36 weeks
- IBS-C participants: ≥ 4 weeks, ≥ 12 weeks, ≥ 24 weeks, ≥ 36 weeks, ≥ 48 weeks, ≥ 52 weeks, ≥ 64 weeks

Treatment compliance is defined as the number of capsules actually taken by a participant divided by the number of capsules expected for the same period multiplied by 100. The information period will be based on the information from 'Exposure Form' of the participant's electronic case report form (eCRF). The number of capsules expected to be

taken in a specific treatment period will be calculated by multiplying the number of days in that period by the number of capsules to be taken per day.

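### The EAIR counts first events up to 30 days after last dose but stops event-free participants' time at last dose, so any post-dose first event inflates the rate per 100 patient-years of exposure

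*SAP*

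**What the plan says.** SAP 9.2.4 divides the number of participants with a given event, each counted once, by total time at risk in years, and multiplies by 100. For the denominator, "The time at risk for a subject without the specific event is the treatment duration". A participant with the event contributes time from first dose to first onset, inclusive. The result is to be read as the expected number of participants with at least one occurrence "per 100 patient-years of exposure to the study drug".

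Two other SAP sections supply the definitions:

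- Exposure, SAP 6.0: "Duration of treatment is defined for each participant as last dose date minus first dose date + 1 in this study".
- Event window, SAP 9.2.1: "an AE that occurs more than 30 days after the last dose of study intervention in LIN-MD-66 will not be counted as a TEAE".

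The EAIR is planned for TEAEs by SOC and PT and for every category of the adverse event overview in SAP 9.2.2: "TEAEs, treatment-related TEAEs, TESAEs, deaths, and TEAEs leading to study intervention discontinuation".

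The protocol's window is shorter. Its section 9.4.1 says "An AE that occurs more than 1 day after the last dose of study intervention in LIN-MD-66 will not be counted as a TEAE". The SAP version history (section 12.0, Table 2) shows that version 2.0 both widened the window from 1 to 30 days and added the EAIR.

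**The concern.** The numerator runs to last dose + 30 days. The denominator stops at last dose for everyone except the few participants who have a post-dose first event. Those participants bring their own post-dose days with them; the event-free participants observed over the same 30 days bring none. A rate built this way is neither an on-treatment rate nor a rate over the 30-day window, and it is higher than either.

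Long-term safety is this study's only primary objective, and the EAIR is the summary that allows for unequal exposure. The error grows as treatment gets shorter, so a dose group with more early stopping would be inflated more, other things being equal. In sparse SOC and PT rows a single post-dose event moves the rate visibly. The category of TEAEs leading to discontinuation should be barely touched, because those events should start by last dose.

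**Working it through.** The documents give no EAIR value, so there is no figure to reproduce. The SAP formula is applied directly.

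**Inputs from the documents.** Treatment duration T is 24 weeks = 168 days (FC) or 52 weeks = 364 days (IBS-C); the post-dose window w is 30 days; a year is 365.25 days (SAP 9.2.4). **Assumed:** a constant hazard λ on drug, a recorded hazard kλ off drug, and no early stopping.

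**Direction.** Suppose there are n on-treatment first events over total time M in days. One further first event, d days after last dose, changes n/M to (n + 1)/(M + d). This is an increase unless the on-treatment rate already exceeds 365.25/d per patient-year. At d = 30 that is 12.175 per patient-year, or 1217.5 per 100, which is implausible here.

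**Ceiling.** For rare events with k = 1 the ratio tends to (T + 30)/T. The excess is 30/168 = 17.9% in FC and 30/364 = 8.2% in IBS-C. If everyone stopped at day 28 it would be 30/28 = 107%.

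**Closed form**, with T and w in years:

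- On-treatment events: A = 1 − exp(−λT), over person-time A/λ.
- Post-dose first events: B = exp(−λT)·[1 − exp(−kλw)].
- Post-dose time of those participants only: C = exp(−λT)·[(1 − exp(−kλw))/(kλ) − w·exp(−kλw)].
- SAP rate: (A + B)/(A/λ + C). The true on-treatment rate is λ.

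For FC with λ = 0.3 per year and k = 1: A = 0.12889, A/λ = 0.42964, B = 0.02120, C = 0.00087. The SAP rate is 0.15009/0.43050 = 0.3486, or 34.86 per 100 patient-years against a true 30.00, an excess of 16.2%.

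The table uses λ = 0.3 per year, with rates per 100 patient-years and a true on-treatment rate of 30.00. To +1 day means events and time both end at last dose + 1 day; to +30 days means both end at last dose + 30 days.

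| k | FC: SAP (excess) | FC: to +1 day | FC: to +30 days | IBS-C: SAP (excess) | IBS-C: to +1 day | IBS-C: to +30 days |
|---|---|---|---|---|---|---|
| 1 | 34.86 (16.2%) | 30.00 | 30.00 | 32.07 (6.9%) | 30.00 | 30.00 |
| 0.5 | 32.45 (8.2%) | 29.92 | 27.87 | 31.04 (3.5%) | 29.96 | 29.02 |
| 0.25 | 31.23 (4.1%) | 29.88 | 26.80 | 30.52 (1.7%) | 29.95 | 28.52 |
| 0.1 | 30.49 (1.6%) | 29.85 | 26.15 | 30.21 (0.7%) | 29.94 | 28.22 |
| 0 | 30.00 (0%) | 29.83 | 25.72 | 30.00 (0%) | 29.93 | 28.02 |

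At k = 1 the excess is 17.6% (FC) and 8.0% (IBS-C) for λ = 0.05 per year, and 12.9% and 4.4% for λ = 1.0.

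**Count example** (group size and events assumed; on-treatment first events at mid-period, one post-dose first event 15 days after last dose):

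- FC, 60 participants, 8 on-treatment events: time = 52 × 168 + 8 × 84 = 9408 days, rate = 8/9408 × 36525 = 31.06. With the post-dose event: 9/9423 × 36525 = 34.89 (+12%).
- IBS-C, 60 participants, 16 on-treatment events: time = 44 × 364 + 16 × 182 = 18928 days, rate = 30.87. With the post-dose event: 17/18943 × 36525 = 32.78 (+6%).

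These examples lie towards the high end. At the on-treatment rate, the FC event-free participants would yield 52 × 30 × 8/9408 = 1.33 post-dose events, so one event corresponds to k of about 0.75. For IBS-C, 44 × 30 × 16/18928 = 1.12, so k is about 0.90.

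**The case against.** The best reply is that events attributed over 30 days, per unit of drug exposure, form a usable descriptive index that errs on the cautious side. SAP 9.2.4 also refers to an analysis period that it does not define; if that meant the treatment period, the mismatch would vanish, and the separate table specifications mentioned in SAP 1.0 might say so. But nothing in the two documents limits EAIR events to on-treatment onset, and the SAP applies the EAIR to every TEAE category under the 30-day definition. The sentence on participants with an event could be read as capping their time at last dose. That makes the rate slightly higher still: in the FC example, 9/9408 × 36525 = 34.94 rather than 34.89.

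The objection on size has more force. Protocol 8.3.2 collects AEs for 30 days after last dose, but at the scheduled timepoints or as observed or spontaneously reported, and the schedule ends at the end-of-treatment visit. It adds that "Investigators are not obligated to actively seek AE or SAE information after conclusion of the study participation". Protocol 8.3.4 makes any later visit conditional: "If a follow-up visit is deemed necessary for appropriate safety surveillance". Recorded post-dose events may therefore be few. Planned duration is the same across dose groups within an indication, so the inflation would be largely shared if stopping and capture are similar. There is no control arm and no inferential testing.

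One can also object that ending EAIR events at last dose + 1 day reverses a deliberate widening of the window, drops late TESAEs and deaths from the EAIR, and leaves the count and the EAIR in one table row based on different participants. These costs are real and call for a footnote. Matching both windows at 30 days avoids them, but it dilutes the rate with time in which events are poorly captured: against the on-treatment rate it is low by 7.1% (FC) and 3.3% (IBS-C) at k = 0.5, and by 12.8% and 5.9% at k = 0.1.

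**Conclusion.** The concern holds. As written, the numerator and denominator of the EAIR cover different windows, and the rate is too high once any first event is recorded after last dose. The direction does not depend on how the time-at-risk sentence is read. The size cannot be fixed from the documents, because it depends on how many first events are recorded off drug. For full-duration participants it runs from zero to a ceiling of 17.9% in FC and 8.2% in IBS-C, with the lower part of the range plausible; early stopping raises the ceiling. The percentages at 0.3 per year rest on an assumed constant hazard and no early stopping. TEAE counts, percentages and listings are unaffected, and no test depends on the EAIR. It should be fixed because it affects the level of a safety rate reported for TESAEs and deaths, and correcting it is cheap.

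**What to change.** In SAP 9.2.4:

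- Restrict EAIR events to first onsets from first dose to last dose + 1 day, which is the protocol's TEAE window. End event-free participants' time at last dose + 1 day; participants with an event still stop at onset.
- Label the rate on-treatment. Add a footnote that its event set differs from the 30-day TEAE counts, and that TESAEs or deaths with later onset appear in the counts and listings but not in the EAIR.
- A matched 30-day version is acceptable as an alternative or sensitivity analysis. Event-free time would run to the earliest of last dose + 30 days, death, loss to follow-up or withdrawal, with the rate reworded as per 100 patient-years at risk. At 0.3 per year it lies about 14% (FC) and 6 to 7% (IBS-C) below the present formula.
- Minor: for TEAEs that qualify by worsening or becoming serious, state that the date of that change is the event date, so that time at risk is at least 1 day. This matters only if a pre-dose onset date would otherwise be used, and the table specifications may already settle it.

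The cost is a few sentences, one footnote and a programming change. At 0.3 per year, reported EAIRs would fall by 0.6% (no post-dose events) to 14% (equal hazard off drug) in FC, and by 0.2% to 6.5% in IBS-C. Against the true on-treatment rate, the revised EAIR is low by at most 0.6% in FC and 0.2% in IBS-C.
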